## Introduction

### Background and Rationale

Compared with other risk factors, elevated BP is associated with more CVD events and BP is associated with more CVD events and disability-adjusted life years lost in the US and worldwide. To identify patients with hypertension and monitor their BP while taking antihypertensive medication, most US guidelines and scientific statements recommend BP be measured in the clinic setting by a trained healthcare professional. This recommendation is supported by extensive data, demonstrating that elevated BP, measured using this approach, is associated with increased risk for CVD and renal disease events. In clinical practice and research studies conducted in the US, BP is almost universally measured in the clinic with an observer present (attended clinic BP).

Several studies have found that compared with attended clinic BP, BP measured outside of the clinic is a better predictor of a person's CVD risk. The US Preventive Services Task Force (USPSTF) and the UK National Institute for Health and Care Excellence recommend that elevated BP measured in the clinic be confirmed by out-of-clinic BP measurements prior to diagnosing hypertension. ABPM is the reference standard for out-of-clinic BP assessment and making the diagnosis of hypertension. ABPM monitors are compact, worn on a belt or in a pouch, and connected to a BP cuff on the upper arm by a tube. The monitors are programmed to obtain readings using the oscillometric method, every 15 to 30 minutes, typically for 24 hours, throughout the day and night.

In some people, there is a transient BP increase that occurs in the clinic setting (i.e., white coat effect). For others, BP is lower in the clinic when compared to measurements obtained outside of the clinic environment (i.e., masked effect). White coat hypertension is defined as hypertension based on clinic- $ma \geq 140$  mm Hg the clinic setting (awake BP  $< 135/85$  mm Hg). In most ABPM studies, white coat hypertension has not been associated with increased CVD risk. In contrast, masked hypertension, defined as not having hypertension based on BP measured in the clinic setting ( $< 140/90$  mm Hg) but hypertension based on out-of-clinic measurements (awake BP  $\geq 155$  mm Hg) is associated with a markedly increased CVD risk. Among adults with SBP/DBP  $\geq 140$  mm Hg white coat hypertension. Additionally, between 15% and 30% of adults with SBP/DBP  $< 140/90$  mm Hg, defined using attended BP measured in the clinic, have masked hypertension.

There is a diurnal pattern of BP, which normally falls to its lowest level during sleep. Nocturnal hypertension, defined by having high mean sleep BP (SBP/DBP  $\geq 120/70$  mm Hg) with an increased risk for CVD events, independent of BP measured in the clinic and awake BP on ABPM. Assessing sleep BP may be particularly important for African Americans, a population with high CVD risk and approximately two times higher prevalence of nocturnal hypertension compared with whites. In the Jackson Heart Study (JHS), a cohort comprised exclusively of African Americans, 60% of participants had nocturnal hypertension and the multivariable-adjusted hazard ratio for CVD events was 1.84 (95% CI: 1.00, 3.38) comparing participants with and without nocturnal hypertension. Also, a high percentage of African Americans with nocturnal hypertension do not have hypertension based on clinic BP or awake BP on ABPM.

Until recently, ABPM has been the only method that could assess sleep BP. The misdiagnosis of hypertension when BP is measured by an observer in the clinic versus by ABPM is well recognized by guidelines, scientific statements, and position papers. However, there are several challenges that have prevented the wide-spread use of ABPM in clinical practice. Recently, we conducted a nominal groups study, a qualitative research approach, with 40 physicians in Alabama and New York to identify barriers to performing ABPM. Reported barriers included need for staff training, time constraints in patient preparation, and lack of infrastructure and inaccessibility of equipment and specialists to whom providers could refer their patients for the ABPM procedure. Also, ABPM devices cost over \$2,000 each, insurance companies do not commonly reimburse for indications other than white coat hypertension, and when reimbursed, the compensation is low.

Low patient tolerability for ABPM has been reported in previous studies. For example, in one study, side effects associated with ABPM ranged from 7% for bruising to 70% for the device awakening the participant during sleep. Given the real world limitations of ABPM, novel approaches are needed for measuring awake and sleep BP. An emerging method that has been proposed for estimating awake BP is to measure BP in the clinic using a fully automated oscillometric device (AOBP) without an observer being present (unattended clinic BP measurement). There are currently two validated oscillometric devices available in the US (Omron HEM-907XL and Microlife's Watch BP office) that can be programmed to measure BP automatically without an observer being present. Using these devices, the technician or healthcare provider leaves the room after a person has a BP cuff placed on their arm and they are positioned for measurements. After a minute rest, the device inflates the cuff and BP is measured. AOBP devices can obtain several BP measurements at preset (e.g., one minute) intervals. The maker of BPTru, a third device, went out of business in 2017.

Canadian studies suggest that patients with hypertension have lower unattended BP compared with attended BP. Therefore, the use of unattended clinic BP may result in a lower prevalence of white coat hypertension. In a pooled analysis of 8558 adults, the mean clinic BP was 10/7 mm Hg lower with unattended AOBP versus BP recorded by a provider in clinical practice by auscultation and a mercury sphygmometer. In the only randomized study of AOBP published to date, the difference between BP when measured observed and unobserved was small (< 5 mm Hg). In 2017, the Hypertension Canada guideline recommended unattended BP (i.e., AOBP) as the preferred method of clinic BP measurement. However, this recommendation was based on a Grade D level of evidence (i.e. quality of evidence is very low, based on expert opinion, no direct research evidence, and studies had very severe limitations). US guidelines do not currently recommend AOBP for use in clinic practice. Recently, in a post-hoc analysis of SPRINT data, there was no difference in clinic BP between sites that measured it unattended versus attended (manuscript under review at Hypertension, personal communication, [name]). At each visit, SPRINT participants did not have both unattended and attended BP measurements; there was no randomization; information about the conduct of unattended or attended BP measurements was obtained retrospectively after study end; and no comparison to ABPM was made. There is currently equipoise as to whether unattended clinic BP provides an accurate estimate of awake BP on ABPM.

Two issues have been raised as barriers to implementing AOBP in clinical practice: the time it takes to perform this procedure and the need for dedicated space. Although AOBP takes longer than unstandardized clinic BP measurement (clinic BP taken without following guideline-recommended approaches), AOBP takes a shorter amount of time than clinic BP measurements taken following American Heart Association (AHA) recommendations. Further,

unstandardized clinic BP measurements are very common in clinical practice, generate poor estimates of BP, and interventions targeted at observers to obtain standardized clinic BP have been largely unsuccessful. Having a dedicated room to perform unattended BP has been reported as a barrier to AOBP. However, if clinic space is not available, unattended AOBP can be successfully performed while a patient is in a waiting room.

Recently, home BP monitors (HBPM) have been adapted to measure asleep BP. As described below, there are compelling preliminary data supporting this approach. Until recently, sleep BP could only be assessed by ABPM. HBPM devices have been developed that measure BP automatically during sleep. These devices have been previously validated for accuracy. Before going to sleep, a person attaches a BP cuff to their arm and turns on the HBPM device, which is programmed to take BP measurements while the person is asleep. In a prior study conducted in Japan, an HBPM device (Omron HEM-5001) was programmed to obtain BP measurements at 2am, 3am and 4am. Given that only three readings are obtained during the sleep period and that a prior study demonstrated the feasibility for measuring sleep BP, there is great potential for using these HBPM devices for accurately measuring sleep BP with less burden than ABPM. Table 3 shows the major limitations of published studies using HBPM to assess sleep BP. In the current study, we will test whether HBPM is an accurate and better tolerated approach for measuring sleep BP than ABPM.

## Objectives

**Primary Aim 1:** To examine whether measuring unattended clinic BP with an automated device will provide a more accurate estimate of awake BP on ABPM than measuring attended clinic BP with an automated device. Hypothesis 1a: The absolute difference with awake BP will be smaller for unattended vs. attended clinic BP. Hypothesis 1b: The agreement between hypertension status using BP measured in the clinic and on ABPM while awake will be higher when clinic BP is measured unattended vs. attended. Also, the prevalence of both white coat and masked hypertension will be lower when measuring unattended clinic BP.

**Primary Aim 2:** To examine whether a new HBPM device provides an accurate approach for measuring sleep BP. Hypothesis 2a: Sleep BP on HBPM will provide an accurate estimate of sleep BP on ABPM. Hypothesis 2b: HBPM will be better tolerated (e.g., less awakening during sleep, pain, bruising) than ABPM.

**Primary Aim 3:** To compare the associations of unattended versus attending clinic BP, unattended clinic BP versus awake BP on ABPM, and sleep BP on HBPM versus ABPM with two markers of end-organ damage, left ventricular mass index (LVMI) and urinary albumin-to-creatinine ratio (ACR). Hypothesis 3a: The association with end-organ damage will be stronger for unattended vs. attended clinic BP. Hypothesis 3b: The association with end-organ damage will be similar for unattended clinic BP and awake BP. Hypothesis 3c: The association with end-organ damage will be similar for sleep BP by HBPM and ABPM.

## **Inclusion and Exclusion Criteria**

### *Inclusion Criteria:*

- Age 19 years or older
- Mean screening systolic blood pressure of 110 to less than 160 mm Hg **or** mean screening diastolic blood pressure of 70 to less than 100 mm Hg

[figure not shown]
### *Exclusion Criteria:*

- Taking antihypertensive medications
- Known to be pregnant
- History of sleep apnea
- History of cardiovascular disease, atrial fibrillation, and/or ventricular tachycardia
- High risk for sleep apnea, scoring 5 or greater on the STOP-BANG questionnaire
- Participants who work overnight shifts (11PM-7AM)
- Inability to wear the ABPM and/or HBPM devices and BP cuffs
- Completed ABPM in the past year
- No permanent residence

**Sites of Recruitment:** Columbia University Medical Center and University of Alabama at Birmingham

**Target sample size:** 315 participants with complete data.

## Study Flow

## Recruitment Procedures

Potential participants will be recruited using flyers and contact cards placed around UAB campus and UAB primary care clinics.

There are three methods in which the participant may be contacted/contact us.

1. If the participant returns the contact card, contact the participant using their preferred method (e.g. - phone call or email).
  - a. If the participant prefers to be contacted via phone, please call them during their **preferred day and time** as indicated on the contact card.
  - b. If the participant prefers to be contacted via email, please refer to the draft email to schedule a screening visit to discuss the study and determine their eligibility (**Appendix 1**).
2. If the potential participant calls in to ask about the study, invite them to a screening visit to determine their eligibility (**Appendix 1**).
3. If the potential participant emails the study ([[contact]](mailto:[contact])), use the draft email (**Appendix 1**) to schedule a screening visit to discuss the study and determine their eligibility.

Once you have confirmed the potential participant is eligible for the study, confirm that the participant will be able to attend all four study visits over a short period of time (within 1-2 weeks). Schedule their first study visit and provide them with a participant packet which will include the following:

1. **Consent Form** – Ask them to read through this carefully but do not sign prior to their first visit.
2. **W9 Form** – Inform them that they will need to fill this out for compensation
3. **Parking decal** for the UAB Hypertension Research Clinic
4. **Directions and a parking map** for the UAB Hypertension Research Clinic

Remind the participants of the following before their first study visit:

1. Please wear a loose fitting shirt or button down shirt with an undershirt so that we can properly place your blood pressure cuff on their bare skin.

2. Refrain from smoking, exercise, eating food, or drinking any caffeinated beverage (including soda and tea) 30 minutes prior to your first clinic visit.

## Participant Scheduling

Following telephone screening, participants who are preliminarily eligible for inclusion in the study should be scheduled within the next **2 weeks** for their screening visit with the study coordinator at the UAB Hypertension Clinic.

**To access the schedule and schedule a participant, please do the following:**

1. Log-in to REDCap using your log-in credentials.
2. In the left-hand column, please select 'Calendar'.
3. Select the 'Month' tab at the top of the calendar.
4. Click on '+New' on a day that has **less than 4 participants scheduled**.
5. Confirm with the participant that they are available on that day.
6. Ask the participant a time they would like to come in for their screening visit and enter the time in the 'Time:' box.
7. In the 'Notes' section, please enter the participant's first and last name.
8. Using the drop-down menu next to 'Record ID', please select the participant's record id number.
9. After you have entered all information, please click 'Add Calendar Event'.

After scheduling the participant, please email or call the study coordinator to inform her of the new participant added to the schedule.

**If the participant needs to re-schedule**, please make the necessary change to the REDCap calendar by clicking on their calendar event and entering their new date and time. Please make sure you save both the new date and new time. Inform the study coordinator of the change to the calendar.

## Summary

During the screening process, participants will complete an initial telephone screening to determine their preliminary eligibility. If eligible, they will be asked to complete a blood pressure screening in the clinic to determine if they are eligible to continue in the study.

There is a consent addendum that was prepared for the Better BP study. Participants will be consented immediately prior to initiation of this study.

Below are the steps to follow for participants who are eligible and consent for the Better BP study.

1. Participants will be randomized to have their clinic blood pressure measured unattended or attended first using a Microlife WatchBP Office AFIB device. Blood pressure will be measured three times in the non-dominant arm following a standard protocol. They will then have their blood pressure measured three times again using the opposite method (i.e. if attended first, then unattended second).
2. The following questionnaires will be administered to participants:
  - a. Sociodemographic/Medical History
  - b. Pittsburgh Sleep Quality Index (PSQI)

Whenever possible, these questionnaires will be self-administered. Research coordinators can administer these questions orally for participants who would otherwise have difficulty completing questionnaires on their own.

3. Measure height, weight, and waist and neck circumference. Neck circumference is needed for the STOP-BANG sleep apnea scale.
4. Participants will then return to the clinic for the next visit in 24 to 48 hours and have their clinic blood pressure measured three times unattended and attended in the reverse order of visit 1 using the Microlife WatchBP Office AFIB device.
5. Participants will be randomized to receive either the ABPM or HBPM device at visit 2.
6. They will be fitted for the device (WatchBP O3 ABPM or WatchBP Home N) that they were randomized to receive first.
7. The staff member will explain how the participant should act when a BP measurement is taken.
8. One measurement will be taken – check to make sure the cuff inflates and deflates and that a valid reading is obtained. Watch to make sure that the participant positions their arm as instructed. If an error reading is obtained, check that the cuff is properly placed and neither too tight nor too loose, and retake the BP measurement. If three consecutive error readings are obtained, try a different device.
9. Participants will be given instructions for placing (Home N) or replacing (O3 ABPM) the device if it has to be removed.
10. Participants will be given a phone number to call if they have any questions during the monitoring period.
11. Participants will be given the appropriate (ABPM or HBPM) device log to fill out. This form captures the time a participant goes to sleep and awakens. Additionally, this form can be used to document any time when a participant removes the device and puts it back on.

12. The Actiwatch device will be fitted.
13. The next day, participants will return the device and device log, complete either the post-ABPM or post-HBPM questionnaire based on what device was worn, and be fitted for the opposite device (either O3 ABPM or Home N).
14. At the last visit, participants will return the device and device log and complete either the post-ABPM or post-HBPM questionnaire based on what device was worn.
15. Participant will complete the comparability questionnaire.
16. Participants will complete a non-fasting blood draw and spot urine.
17. Participants will complete an echocardiogram. If the echo lab does not have availability for that day, schedule their echocardiogram within the next two weeks.

Participants will return to the clinic the next day to return their ABPM/HBPM devices and actigraphy (Actiwatch) devices and the participant device log.

Upon returning the devices, the technician will:

1. Review the device log with the participant, verifying times the participant went to sleep, woke up, and took device(s) off. If the participant does not return the device log (or it is blank), be sure to fill it out at the return visit.
2. Download the data from the ABPM, HBPM, and actigraphy devices.
3. Confirm that at least 35 of planned ABPM readings are valid or all three HBPM readings are valid. If this is not the case, the participant will be offered the opportunity to complete a second ABPM or HBPM (along with actigraphy and filling out the participant device log).

For participants who have a complete ABPM (or for those who have the device picked up at their house), the participant device log will be checked for completeness, scanned and saved electronically. Next, we will administer the post-ABPM study visit form.

Upon completion of the physical exam and echocardiogram, we will then process their reimbursement. The participants will receive reimbursement through the mail.

**When clinic staff will handle the return of the ABPM/HBPM:**

For participants for whom the device is picked up at their house or who mail in the device, the forms/device will be delivered to the clinic staff. The staff member will check to confirm that at least 35 valid ABPM readings or 3 valid HBPM readings were obtained and that the post-ABPM questionnaire has been completed. If  $\geq 35$  valid ABPM readings are obtained, they will be processed as described in the manual of procedures.

## Overview of Better BP Study Visits

The Better BP study involves five visits. Ideally, all five visits will occur within 24-48 hours of each other. For some participants the next visit will not occur within this timeframe; however, the next visit should be scheduled as soon as possible.

The screening visit will take approximately 10 minutes to conduct including signing of the consent form and blood pressure screening. If eligible, the participant will continue on with their first study visit.

The first study visit will take approximately 45 minutes to conduct including the initial five-minute rest prior to obtaining clinic blood. This visit includes confirming eligibility, obtaining three clinic blood pressure measurements both attended and unattended (randomized order), and completing two questionnaires (Sociodemographic/Medical History and Pittsburgh Sleep Quality Index). The visits for this study will be conducted in a separate room or, at minimum, in an area properly screened from all other activity and participants in the UAB Hypertension Research Clinic.

The second study visit will include an additional three clinic blood pressure measurements, both attended and unattended, in the reverse order of visit 1 and fitting the participant for the ABPM or HBPM device (randomized) and Actiwatch.

The third study visit will include the participant returning their device (ABPM or HBPM) and device log, confirmation that an adequate number of blood pressure readings were obtained, and completion of a post-ABPM or post-HBPM questionnaire (based on the device worn previously). The participant will then be fitted for the opposite device (either ABPM or HBPM) and receive a device log.

The fourth study visit will include the participant returning their device (ABPM or HBPM) and device log, confirmation that an adequate number of blood pressure readings were obtained, and completion of a post-ABPM or post-HBPM questionnaire (based on the device worn previously). They will also complete the comparability questionnaire. The participant will have a brief physical exam which includes a non-fasting blood draw and spot urine collection. Finally, the participant will complete an echocardiogram. Upon completion of the echocardiogram, participants will receive reimbursement through the mail.

## **MOP items**

### **Initial visit**

Information from this visit will be recorded on the Better BP study Visit 1 Data Collection Form.

- 1. Consent participant and measure screening blood pressure to confirm participant eligibility.**
- 2. Measure height, weight, and waist and neck circumference.**
- 3. Take non-dominant arm circumference measurement.**
- 4. Identify randomization assignment for unattended and attended clinic BP measurement.**
- 5. Clinic BP measurements (unattended and attended, in randomized order).**
- 6. Questionnaire administration:**
  - a. Sociodemographic/Medical History**
  - b. Pittsburg Sleep Quality Index (PSQI)**

### **Visit 2**

Information from this visit will be recorded on the Better BP study Visit 2 Data Collection Form.

- 1. Clinic BP measurements (reverse order of study visit 1).**
- 2. Identify randomization assignment for ABPM and HBPM.**
- 3. ABPM or HBPM fitting and guidance (based on randomization).**
- 4. Actiwatch fitting and guidance.**

### **Visit 3**

Information from this visit will be recorded on the Better BP study Visit 3 Data Collection Form.

- 1. Download ABPM or HBPM and Actiwatch data and check completeness.**
- 2. Review device log with participant for completeness and accuracy.**
- 3. Complete post-ABPM or post-HBPM questionnaire (based on device worn).**
- 4. ABPM or HBPM fitting and guidance (opposite device of visit 2).**

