## Actiwatch\*

The Actiwatch database is updated with each new participant's downloaded data. Before starting the study (before the first participant), the database should be saved onto a network drive that is backed up daily. This is done by selecting File → Database → New. Then the Database should be saved into the appropriate location.

[figure not shown]
1. Place Actiwatch device onto the charger.
2. Launch Philips Actiware 6 software.
3. In the Actiwatch software window, click "Communications" on the Menu Bar at the top of the window and then select "Actiwatch Communications Console".

[figure not shown]
4. Select the “Actiwatch 2” device (the participant’s ID number should be located under the “Actiwatch 2”). Click the “Retrieve” button at the bottom of the window.

5. Make sure that the “Launch Actogram” check box is selected. Then select the “Save Data” button.

[figure not shown]
6. Make sure the radio button for “Put Actiwatch to sleep for later use” is selected and then click “Next”. Then select “Put Actiwatch to Sleep” (if this message comes up).

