## **Better BP Study Visit 2 Checklist**

- [ ] COVID-19 Screening [ ] Yes [ ] No
- [ ] Symptom Tracker
- [ ] Temperature Check
  
- [ ] Confirm that participant has avoided caffeinated products, food, smoking, and exercise for at least 30 minutes prior to this visit.
- [ ] State Anxiety Index (Opposite of Visit 1)
  - [ ] Unattended [ ] Attended
- [ ] Clinic BP measurements: (order will be opposite of Visit 1)
  - [ ] Attended then Unattended
  - [ ] Unattended then Attended
- [ ] Randomization 2
  - [ ] ABPM device
  - [ ] HBPM device
- [ ] Actiwatch activity monitor device  
(Actiwatch device will be removed at visit 4)
- [ ] Provide participant with the assigned Device Log form
- [ ] Provide participant with State Anxiety Index for home  
(To be completed during night of monitoring)

Completed By \_\_\_\_\_

Date \_\_\_\_\_

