## **Better BP Study Visit 3 Checklist**

[ ] COVID-19 Screening [ ] Yes [ ] No

[ ] Symptom Tracker

[ ] Temperature Check

[ ] Device return

[ ] Check the device for complete readings

[ ] HBPM three sleep BP readings [ ] Yes [ ] No

[ ] ABPM ~35 measurements [ ] Yes [ ] No

If No, ask participant to wear the device again to collect all necessary readings or measurements.

If yes, complete the Post Questionnaire (**circle one**: email or in-person)

[ ] Post ABPM Questionnaire

[ ] Post HBPM Questionnaire

[ ] Participant will wear the opposite monitor of Visit 2

[ ] ABPM device

[ ] HBPM device

(Actiwatch device will be remove at visit 4)

[ ] Provide participant with the assigned Device Log Form

[ ] Provide participant with State Anxiety Index for home

(To be completed during night of monitoring)

Completed by \_\_\_\_\_ Date \_\_\_\_\_

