**Table 4. Domains of data collection**

1. Unattended clinic BP
2. Attended clinic BP
3. 24-hour ABPM with actigraphy
4. One night of HBPM with actigraphy
5. Questionnaires including HBPM and ABPM tolerability
6. A brief physical examination
7. Spot urine to assess albuminuria
8. Transthoracic echocardiogram

ABPM monitor and actigraph removed. Data will be downloaded onto computers dedicated to the current study. The ABPM recording will be checked for completeness. If a complete recording is not obtained, participants will be asked to repeat the ABPM procedure. Once a complete ABPM is confirmed, participants will fill out the ABPM tolerability questionnaire (**Section D.8.5**). This questionnaire will be self-administered unless participants are unable to read, in which case, it will be interviewer administered. Participants will be given an HBPM device and instructed in its use as described in **Section D.8.4.3**.

**D.6.3.2. Participants randomized to undergo HBPM then ABPM.** At Study Visit 3, participants will return the HBPM device and have the actigraph removed. Data will be downloaded onto computers dedicated to the current study and the recording will be checked for completeness. Next, participants will be asked to fill out a questionnaire on the tolerability of HBPM (**Section D.8.5**). This questionnaire will be self-administered unless participants are unable to read, in which case, it will be interviewer administered. Participants will be fitted with an ABPM device and instructed in its use as described in **Section D.8.4.2**.

**D.6.4. Study Visit 4.** Identical activities will occur at Study Visits 3 and 4 (i.e., the ABPM or HBPM devices will be returned, checked for a complete recording, and a tolerability questionnaire will be filled out). At the conclusion of Study Visit 4, participants will be escorted by study staff to the laboratory for an echocardiogram. Upon completion of the echocardiogram, participants will have successfully completed the study.

Figure 3. Activities conducted at a screening visit and the four study visits.

Screening visit	Visit 1	Visit 2	Visit 3	Visit 4

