#### **D.10.2. Data transfer.**

**D.10.2.1. ABPM, sleep HBPM, actigraphy, and Device Logs.** Upon return of the ABPM, HBPM, actigraph, and Device Logs, data will be downloaded to a computer and then backed up to a secure network server. Data will be transferred daily to the PEER Unit at UAB using DatAnywhere, a HIPAA compliant file transfer protocol that we used in our AHA-SFRN study. Monthly reports that track data quality will be generated. If data issues are identified (e.g., frequent ABPM or HBPM reading errors), staff will be re-trained.

**D.10.2.2. Echocardiographic measures.** The echocardiographic studies (with unique study identifiers; i.e. de-identified) will be saved to DVD/CD, and backed up to secure research servers at each site. The studies at UAB will be sent to the Cardiovascular Physiology Research Laboratory at Columbia for analysis.

**D.10.3. Data management and cleaning.** All data cleaning will be managed by a statistician at the UAB PEER Unit supervised by [name]. A uniform data editing algorithm, established by Drs. [name] and [name] and used in prior studies, will be implemented to confirm acceptability of the ABPM data and exclude extreme outliers. Minimal editing is the general rule; less than 0.1% of readings are typically excluded. The awake and sleep periods on ABPM will be defined by the actigraphy recording, complimented by self-report

awake and sleep periods from the Device Log. For sleep BP on HBPM, we will confirm that participants were asleep when the the BP readings were obtained using actigraphy data and the HBPM Device Log.

**D.10.4. Minimum number of BP readings required on ABPM and HBPM.** No consensus exists on the number of readings required to consider an ABPM recording complete. Consistent with our prior studies, we will require 14+ awake BP readings, and 5+ sleep BP readings, and  $\geq 80\%$  of the planned 48 readings (39+ total valid readings). We will require three SBP and DBP readings for a sleep HBPM recording to be complete. We will continue recruitment until 600 participants have complete ABPM and sleep HBPM readings.

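### The manual's Visit 3 instructions for the Actiwatch conflict, so literal compliance could end recording before the second night, although the protocol uses actigraphy on both nights

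*Combined protocol and SAP*

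**What the plan says.** **Manual, visit lists.** Visit 2 includes "Actiwatch fitting and guidance". Visit 3 starts with "Download ABPM or HBPM and Actiwatch data and check completeness" and its last step is "ABPM or HBPM fitting and guidance (opposite device of visit 2"; it has no Actiwatch step after the download. Visit 4 lists an Actiwatch download again.

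**Manual, Actiwatch download.** This is the only download procedure. At step 6 staff select "Put Actiwatch to sleep for later use", with no exception for Visit 3. The returns section has the watch brought back the day after each monitoring period, and the storage section has it wiped, charged and stored after download.

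**Manual, configuration.** The data collection duration is set to 7 days. The preceding step asks for a maximum recording time of at least 3 days.

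**Checklists.** Visit 2: "Actiwatch device will be removed at visit 4". Visit 3: "Actiwatch device will be remove at visit 4". The Visit 4 checklist has the removal item.

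**Protocol.** In D.6.3.2, "participants will return the HBPM device and have the actigraph removed"; D.6.3.1 does the same for the ABPM-first order. Both then refer to the section on the next device (D.8.4.2 or D.8.4.3), and each of those fits an Actiwatch. D.10.3 says: "The awake and sleep periods on ABPM will be defined by the actigraphy recording, complimented by self-report" from the device log. For HBPM, D.10.3 uses actigraphy and the log to confirm that the participant was asleep at the readings.

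**The concern.** Three accounts of the watch at Visit 3 stand side by side: downloaded and put to sleep, left on until Visit 4, and removed then refitted. Under the first, taken literally, the participant goes home for the second night with a watch that is no longer recording.

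The second night is HBPM for participants randomised to ABPM first, and ABPM for those randomised to HBPM first. If it had no actigraphy, the ABPM-first group would have actigraphy-defined ABPM sleep and log-only confirmation for HBPM. The HBPM-first group would have log-only ABPM sleep and actigraphy-confirmed HBPM. The way sleep is determined would then depend on device order within the paired Aim 2 comparison. The analysis plan restricts its sleep comparison to participants with complete sleep BP data, but it does not mention actigraphy or say how a night without it is handled.

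**Working it through.** **1. Would one recording cover both nights?** The visit overview aims for 24 to 48 hours between visits, so Visit 2 to Visit 4 spans about 2 to 4 days. That fits a 7-day recording. It does not always fit the 3-day minimum for maximum recording time, which falls short if both gaps are 48 hours. In the usual case the risk comes from the put-to-sleep step, not from the configured duration.

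**2. Is there a restart at Visit 3?** The Visit 3 list, checklist and data collection form contain none. There is an indirect route. The ABPM and HBPM fitting procedures serve Visits 2 and 3, each ends by showing the participant how to remove and replace the Actiwatch, and the fitting and configuring sections for the watch follow. A coordinator may get there, but no Visit 3 step says so.

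**3. How large could the effect be?** The plan gives no figure for this, so none can be reproduced. Inputs:
- Table 1 of the analysis plan, overall ABPM means: awake 118.7/74.2, asleep 104.1/60.3 mm Hg. Difference: 118.7 − 104.1 = 14.6 and 74.2 − 60.3 = 13.9.
- Assumption, not in the documents: the log counts 30 to 60 more wakeful minutes as sleep than actigraphy does, in an 8-hour (480-minute) night.
- Assumption: those minutes carry the full awake ambulatory mean. Quiet wakefulness in bed may not reach it, so this is an upper-end choice.

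Shift in mean ABPM sleep BP where ABPM is the second night = difference × minutes / 480:

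| | 30 min | 60 min |
|---|---|---|
| Systolic | 14.6 × 30/480 = 0.91 | 14.6 × 60/480 = 1.83 |
| Diastolic | 13.9 × 30/480 = 0.87 | 13.9 × 60/480 = 1.74 |

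Only the HBPM-first order (301 of 603, about half) is exposed in this way. The HBPM mean comes from three fixed readings, and loss of actigraphy removes a check on those readings without redefining the mean. The pooled shift in the ABPM-versus-HBPM difference, if every second night were lost, is therefore about half:
- systolic 0.91/2 = 0.46 to 1.83/2 = 0.91 mm Hg
- diastolic 0.87/2 = 0.43 to 1.74/2 = 0.87 mm Hg

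D.12.2.1 aims to exclude 2.1 mm Hg systolic and 1.4 mm Hg diastolic. Both pooled ranges lie below these. Partial loss scales them down in proportion.

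**4. Do the reported means show it?** Table 1 gives ABPM sleep systolic BP of 103.4 on the second night (HBPM-first) and 104.7 on the first: 103.4 − 104.7 = −1.3. With SDs of 10.3 and 10.6 and 301 and 302 participants, the standard error is √(10.3²/301 + 10.6²/302) = 0.85, giving a 95% interval of about −3.0 to 0.4. HBPM also falls on the second night: 105.7 − 106.9 = −1.2. The diastolic changes are 60.1 − 60.4 = −0.3 (ABPM) and 61.8 − 62.9 = −1.1 (HBPM). No systolic excess is visible on second-night ABPM. These are comparisons between different participants that also carry any second-night effect, so they neither show nor exclude a loss of actigraphy.

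**The case against.** The strongest case is that the documents plainly intend second-night actigraphy and give staff a way to obtain it. Visit 4 has its own Actiwatch download, the checklist used at Visit 3 places removal at Visit 4, and the fitting procedures lead into the watch instructions. This stands. It makes loss a possibility under literal compliance, not the expected result.

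A reader might infer from D.6.3 that the protocol itself sends participants home without a watch. It does not: the same paragraphs hand over to sections that fit one. A reader might also take the missing Actiwatch line on the Visit 3 form as proof. The Visit 2 form has no configure or start line either, and there the fitting is undisputed.

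The dependence on actigraphy is also softer than it first looks. D.10.3 pairs it with the device log on both nights, and the manual's ABPM download step sets awake and asleep times from the log. If the analysed ABPM means came from those log times, losing actigraphy would not change them. The analysis plan does not say which source was used, so this limits the concern without closing it.

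Finally, 603 participants are already tabulated, so a manual edit comes too late for them. That is fair. Only the analysis part can still change these results.

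**Conclusion.** The instructions conflict and should be reconciled. Following the Visit 3 list and the download procedure literally would stop the watch before the second night, contrary to the checklists and to the use of actigraphy in D.10.3.

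The consequence is modest. Under the stated assumptions, and with every second night lost, the pooled Aim 2 difference shifts by about 0.5-0.9 mm Hg systolic and 0.4-0.9 mm Hg diastolic. This also assumes that actigraphy, not the log, would otherwise have set the ABPM sleep window.

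A reader might go further and infer that second nights were in fact lost, or that the HBPM-versus-ABPM result is biased by device order. The documents do not support either. They give no count of nights with or without actigraphy. The unhalved figures of 0.9-1.8/0.9-1.7 mm Hg apply to one order only and should not be set against the full-sample 2.1/1.4 mm Hg.

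**What to change.** **Manual and protocol.** Reconcile the Visit 3 list and the download procedure with the Visit 2 and Visit 3 checklists and D.6.3. There are two options:
- Drop the Actiwatch download at Visit 3 and record continuously to Visit 4, with the maximum recording time checked against the actual visit spacing.
- Keep the download and add a step at Visit 3 to reconfigure, start and refit the watch, in both the list and the form.

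**Analysis.** Report the number of participants with usable actigraphy by night and by device order. State which source defines the ABPM sleep window. Where second-night actigraphy is missing, define sleep by the device log on both nights in the paired Aim 2 comparison, so that each participant's two devices share one definition.

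**Cost.** A few lines in the manual and protocol, one count table, and a sentence or two in the analysis plan. With continuous recording, first-night actigraphy is checked one visit later. Under the analysis rule, some recordings rest on self-reported sleep times.
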